5.5.4 Vital signs

All vital signs will be listed.

5.5.5 12-Lead ECG

Mean values of 12-Lead ECG results will be taken at each visit. ECG data include: HR (beats/min), PR interval (ms), QT interval (ms), and QTcF (ms).

ECG parameters measured at the study site will be summarized as follows:

- Maximum PR interval \geq 300 ms
- Maximum QT interval \geq 500 ms
- Maximum QTcF interval (ms) (450–<480, 480–<500, or \geq 500)
- Maximum QTcF interval \geq 480 ms or increase $>$ 60 ms from baseline

Related data will also be listed.

5.5.6 ECOG PS

All ECOG PS will be listed.

5.5.7 Physical examination

Data of physical examination will be listed.

5.5.8 Other safety measures

Echocardiography will be listed by treatment group and time.

Pregnancy test results will be listed by treatment group and time.

Observation results of reactive capillary endothelial proliferation will be listed.

The subjects' virological examinations will be listed.

5.6 Pharmacokinetic Analysis

The drug concentrations of SHR-1210 and apatinib will be statistically described by time point.

5.7 Other analyses

A statistical analysis will be performed according to the confirmatory results of immunogenicity.

The number and percentage of subjects who are ADA positive at baseline, ADA negative at baseline and positive post baseline, and ADA positive for at least once at baseline or post baseline will be summarized using descriptive statistics.

For the population who are ADA negative at baseline and positive post baseline, the following items will be analyzed: the time to the first positive ADA result, the number and percentage of subjects with transient positive post-baseline results (transient ADA positive is defined as the subjects who are negative at baseline and have only one ADA-positive sample post baseline before the last sample and are not persistent ADA positive), the number and percentage of subjects with persistent positive post-baseline results (persistent ADA positive can be divided to two categories: 1) negative at baseline, there are at least two positive samples post baseline, where the first and last ADA-positive samples are separated by a period >16 weeks, or 2) negative at baseline, the last post-baseline sample is positive, or the last post-baseline sample is negative and the second last post-baseline sample is positive), and the number and percentage of subjects with other positive post-baseline results (other ADA positive is defined as the subjects who are negative at baseline, have at least two ADA positive samples post baseline, but not persistent ADA positive, and the last sample is negative).

The number of ADA positive and negative subjects will be summarized and analyzed, and the efficacy and safety of ADA positive and negative subjects will be analyzed to investigate the impact of ADA on efficacy and safety. ADA-positive subjects are subjects with post-baseline ADA-positive samples, mainly including: a. the subjects who have the baseline negative and post-baseline positive samples, or b. the subjects who have both baseline and post-baseline positive samples, and the titer of the post-baseline samples is ≥ 4 -fold of the baseline titer. ADA-negative subjects are those who are not ADA positive.

In addition, the positive ADA results of the subjects producing neutralizing antibodies (Nab) will be summarized and analyzed. Nab-positive subjects are defined as the subjects who have post-baseline Nab positive samples (but those who have baseline and post-baseline Nab positive samples will be classified as Nab inconclusive subjects), and Nab-negative subjects are those who do not have post-baseline Nab positive samples.

Immunogenicity raw data will be reported in the form of listing.

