[21] Pharmacokinetics/immunogenicity test: Blood sampling time points for pharmacokinetics and immunogenicity study of SHR-1210: within 0.5 h pre-administration on C1D1, C2D1, C4D1, C6D1, C9D1, and every 4 cycles thereafter, with 4-6 mL of peripheral venous blood collected at each time point; 4-6 mL of peripheral venous blood will be collected once at 30 days after the last dose. Blood sampling time points for pharmacokinetics study of apatinib: within 0.5 h pre-administration and 4 h (\pm 10 min) post-administration on C1D1, C2D1, C4D1, and C6D1, with 2-4 mL of peripheral venous blood collected at each time point. The time interval between the administration of apatinib on the day of blood sampling and the previous administration should be no less than 20 h.

[22] Quality of life scoring: Performed within 7 days before the first dose, on day 1 of every 2 cycles from cycle 3 onwards, on day 1 of every 4 cycles from cycle 17 onwards, and at 30 days after the last dose.

- [23] Diary card dispensing, retrieval, and filling: The subjects will measure blood pressure by themselves or others during the treatment period, and shall fill out the diary card every day to record blood pressure and other discomforts.
- [24] Safety follow-up: performed on days 30, 60, and 90 after the last dose. The first safety follow-up visit (day 30) will be carried out at the study center, where the evaluations specified in the protocol will be completed. The second (day 60) and the third (day 90) follow-ups will be performed via phone calls. Information on new anti-tumor treatment, survival, concomitant medications/treatments, and adverse events will be collected.
- [25] Survival follow-up: At the end of the safety follow-up period, the subjects will enter the survival follow-up period until death, lost to follow-up, withdrawal of informed consent or termination of the clinical study by the sponsor. During this period, follow-up will be conducted via phone calls or other effective methods once every 2 months to collect information on subject survival and subsequent treatments (if the subjects start a new anti-tumor treatment, the therapeutic regimen and the start and end time should be recorded).

2 FLOW DIAGRAM OF EXPERIMENT — CONTROL GROUP (DOXORUBICIN + IFOSFAMIDE OR IFOSFAMIDE MONOTHERAPY)

STUDY PROCEDURES	Screening Period		Cycle 1	Cycles 2-6	Cycles 7-16	Cycle 17 and beyond	Safety Visit ^[22]	Survival Follow- Up ^[23]

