6.1.3 Exploratory objectives

- To explore the correlation between the immunogenicity and the efficacy/safety of SHR-1210;
- To explore the correlation between the concentrations of SHR-1210 and apatinib and the efficacy/safety;
- To evaluate the investigator-assessed PFS, ORR, DoR and DCR (as per iRECIST) in the SHR-1210 plus apatinib group;
- PFS after crossover treatment of subjects in the doxorubicin plus ifosfamide group (as per RECIST v1.1 and iRECIST);
- To evaluate the ORR, DoR, and DCR (as per RECIST v1.1 and iRECIST), OS, safety, and quality of life scores of subjects in the doxorubicin plus ifosfamide group after crossover treatment.

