2.3 Sample Size

In this study, IRC-assessed PFS will be used as the primary endpoint for superiority test with the control group. An interim analysis will be performed to determine the efficacy of the drugs and to determine whether to terminate or continue the study. The parameters for sample size calculation are as follows:

- Enrollment rate = 13 subjects/month (156 subjects/year), enrollment time = 20 months (the overall time will be 26 months)
- Randomization in a 1:1 ratio; one-sided $\alpha = 0.025$; the power of the test is 90%;
- Hazard ratio (treatment group/control group [HR]) = 0.64 (estimated median PFS is 4.5 months in the control group and 7.0 months in the treatment group)
- An interim analysis will be performed when 67% of PFS events (143) are collected to determine whether the drug is effective or ineffective, and to decide whether to terminate or continue the study.

Based on the above parameters, at least 214 PFS events shall be collected according to the log-rank test for PFS comparison in the two groups and the O'Brien & Fleming spending function (EAST6.4.1) in the α spending function method proposed by Lan-DeMets, i.e., approximately 262 subjects are needed. Considering a 10% dropout rate, 292 subjects are finally required for enrollment.

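### The exploratory ADA comparison in SAP 5.7 is biased toward longer PFS in ADA-positive subjects unless ADA appears almost entirely by the first post-baseline sample

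*SAP*

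**What the plan says.** The first exploratory objective (Protocol 6.1.3, repeated in SAP 2.2.3) reads "To explore the correlation between the immunogenicity and the efficacy/safety of SHR-1210". Protocol 14.4.9 plans only descriptive statistics for ADA. SAP 5.7 goes further and states that "the efficacy and safety of ADA positive and negative subjects will be analyzed to investigate the impact of ADA on efficacy and safety". The rules behind that comparison are:

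- **Grouping (SAP 5.7).** "ADA-positive subjects are subjects with post-baseline ADA-positive samples". A baseline-negative subject needs one positive post-baseline sample; a baseline-positive subject needs a titer at least 4 times baseline. There is no time limit, and everyone else is ADA negative.
- **Sampling (Protocol section 1, footnote 21, and 9.1.1).** "within 0.5 h pre-administration on C1D1, C2D1, C4D1, C6D1, C9D1, and every 4 cycles thereafter", plus one sample 30 days after the last dose. Immunogenicity samples are still taken if SHR-1210 is interrupted.
- **End of treatment (Protocol 8.3.2, 8.3.3).** Treatment normally stops at investigator-assessed progression; some subjects may continue beyond it.
- **Time origin (SAP 4.1.1.1).** PFS is counted from randomization.
- **Analysis set (SAP 5.1.1).** A baseline result and one post-baseline result are enough, so early progressors stay in.

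For the positive-versus-negative comparison, the SAP names no landmark, time-dependent covariate or exposure adjustment. It does derive when baseline-negative subjects first turn positive.

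**The concern.** ADA status is fixed by what happens after the PFS clock has started. To be classed positive, a subject must remain under observation until a sample turns positive, and the number of samples grows with time on treatment. Early progressors are mostly put in the negative group because they were tested less often. This is immortal-time bias, and it comes from the stated grouping rule rather than from a missing detail.

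The SAP frames the comparison as a question about the impact of ADA. If antibodies reduce efficacy, the bias works against seeing it, and ADA can look harmless or protective. For safety, longer observation raises both the number of ADA samples and the number of AEs, so AE incidence may look higher in ADA-positive subjects with no causal link.

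**Working it through.** **1. Inputs.** The SAP (2.3 Sample Size) gives "estimated median PFS is 4.5 months in the control group and 7.0 months in the treatment group", 20 months of accrual in 26 months overall, and "Randomization in a 1:1 ratio", so 292 / 2 = 146 investigational subjects. The documents give no figure for the ADA comparison, so the sample size was reproduced to confirm the inputs:

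- Fixed-design events: 4 × (1.960 + 1.282)² / (ln 0.64)² = 42.03 / 0.1992 = 211.0, i.e. 212. With one Lan-DeMets O'Brien-Fleming look at 143/214 this becomes 213.5, i.e. 214.
- Mean event probability with exponential PFS and uniform accrual is 0.818; 214 / 0.818 = 261.5, i.e. 262; 262 / 0.90 = 291.1, i.e. 292.

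All three stated figures (214, 262, 292) are reproduced.

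**2. Samples by time on treatment.** With 21-day cycles, on-treatment post-baseline samples fall at weeks 3, 9, 15 and 24, then every 12 weeks (36, 48, and so on).

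- Stopping at week 6: 1 on-treatment sample + the 30-day sample = 2.
- Stopping at week 52: 6 + 1 = 7.

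If each sample has the same chance p of being the first positive (an assumption), the chance of being classed positive is 1 − (1 − p)^k for k samples:

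| p | k = 2 | k = 7 |
|---|---|---|
| 2% | 4.0% | 13.2% |
| 5% | 9.8% | 30.2% |
| 10% | 19.0% | 52.2% |

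No ADA effect enters this table. The difference comes only from time on treatment.

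**3. Simulation with no true ADA effect.** Exponential PFS, median 7.0 months; ADA independent of PFS; protocol sampling until progression or 2 years, plus the 30-day sample. Expected values use 200,000 subjects; chance results use 600 replicates of 146. ADA incidence and onset are assumed and varied.

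| ADA onset | Expected HR, ever vs never positive | HR below 1 | Nominally significant longer PFS |
|---|---|---|---|
| Constant chance per sample, 2–20% | 0.62–0.43 | 93–100% | 23–99% |
| Constant hazard, 5–40% cumulative by week 52 | 0.53–0.44 | 88–100% | 8–97% |
| Within the first 15 weeks, 10–40% susceptible | 0.86–0.81 | 66–85% | 2–17% |
| All present at first post-baseline sample | 0.99–1.01 | 49–54% | 1–2% |

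At 5% per sample, 22% of subjects are ever positive, with median PFS 10.8 against 6.0 months. A repeat run gave 0.58, 0.58 and 0.52 at 3%, 5% and 10% per sample, 0.87 for onset within 15 weeks, and 1.00 for the last scenario. Omitting the 30-day sample strengthens the bias (0.82–0.73 for onset within 15 weeks). Also stopping sampling at the data cut moves the figures a few hundredths toward 1.

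**4. Corrected analyses on the same data.** The true HR is 1. A week-15 (C6D1) landmark gave 0.97–1.05 and a time-dependent ADA covariate 0.95–1.08; in the repeat run the two methods gave 0.92–1.01. The departures from 1 are simulation noise.

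**5. Cost of the landmark.** C6D1 is day 105, or 105 / 30.4375 = 3.45 months. S = exp(−ln 2 × 3.45 / 7.0) = 0.71, so about 29% have an event first and 146 × 0.71 ≈ 104 remain. At 5% per sample, 1 − 0.95³ = 14.3% of these, about 15 subjects, are positive by then.

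**6. AEs.** With an assumed AE hazard of 3% per month unrelated to ADA, AE incidence was about 31% in ever-positive subjects against 23–25% in the others, purely from longer observation.

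**The case against.** The strongest reply has four parts.

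- **Onset is unknown.** A reader might infer that the comparison will certainly show longer PFS in ADA-positive subjects, with an HR of 0.5 to 0.6. The documents do not support this. They give neither incidence nor onset of ADA; the bias is modest if onset is confined to 15 weeks and absent if all ADA is present at the first sample. With few positives, one trial can also go the other way by chance. This part stands and limits what can be claimed about size.
- **No method is named.** SAP 5.7 speaks of efficacy and safety, without naming PFS or a model. That is true, but PFS is the primary efficacy endpoint, and the grouping rule is explicit. ORR and DCR share the difficulty, because responders tend to stay on treatment and be sampled longer.
- **The simulation is simpler than the trial.** It ends sampling at the PFS event. In the protocol, treatment can continue past progression, discontinuation follows the investigator while primary PFS follows the IRC, some subjects stop for toxicity, and crossover controls are also sampled. These points make the size less certain. They do not remove the link between time on treatment and number of samples.
- **The analysis is exploratory.** It carries no alpha and no decision rule, and the SAP (section 1) describes itself as an initial version to be finalised before database lock. That limits the importance, and also means the wording can still be changed cheaply.

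A reader might also infer that a C6D1 landmark should replace the whole comparison. For safety it should not: AEs from cycles 1–5 would be lost, including any early grade 3 or higher infusion reactions, which Protocol 13.4 lists as of special interest.

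**Conclusion.** The point holds as a bias in a stated rule, of uncertain size. The ever-positive versus never-positive comparison favours longer PFS in ADA-positive subjects unless ADA appears almost entirely by the first post-baseline sample. With no true effect, the expected HR is about 0.43–0.62 for onset spread over follow-up, 0.81–0.87 for onset within 15 weeks, and about 1.0 for ADA all present at the first sample. These figures rest on exponential PFS with the planned 7.0-month median, the protocol's sampling times, sampling that ends with the PFS event apart from the 30-day sample, and assumed ADA patterns. In none of these scenarios did the expected HR lie meaningfully above 1, so the bias can hide a loss of efficacy from ADA but is unlikely to create one. The AE comparison may be distorted in a similar way; the AE figures are an illustration under one assumed rate. The primary PFS comparison and its type I error are not affected.

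**What to change.** In SAP 5.7:

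1. Analyse PFS by ADA in a Cox model with ADA status as a time-dependent covariate: negative until the first qualifying sample, positive from then on. The time of first positivity is already derived for baseline-negative subjects; for baseline-positive subjects, add the date of the first sample with the 4-fold rise. A sample that first turns positive after the PFS event does not change status in this model.
2. Add a C6D1 landmark as a sensitivity analysis: status from samples up to C6D1, subjects still event-free and in follow-up then, PFS counted from that date.
3. Keep all AEs, including those before C6D1, and compare them as exposure-adjusted rates by time-varying ADA status, so that events before the first positive sample count in ADA-negative time.
4. Keep the ever-positive versus never-positive tables as description only, with a note that they do not estimate the impact of ADA.

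The cost is SAP wording and slightly more programming, with no new data collection. The landmark analysis is less precise, since about 29% of subjects have an event before week 15 under the planned median. Positivity is dated by the sample and not by true onset, which is a limitation to state with the results.

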6 INTERIM ANALYSIS

No interim analysis will be conducted for this study.

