Criteria for Treatment Discontinuation	
Criteria for treatment discontinuation are as follows:
 
 1. Treatment discontinuation requested by subjects; 2. Radiographic or clinical features indicate progression, except for the following two situations: 1) The subject in the investigational treatment group meet the criteria for treatment beyond progression (see 8.3.3 for details); 2) The subject in the control group who had radiographic progression and meet the inclusion/exclusion criteria may be cross over to receive the SHR-1210 + apatinib treatment (see 8.3.4 for details);; 3. Occurrence of subject pregnancy during the study; 4. Any clinical AEs, laboratory abnormalities, or other medical conditions indicating that the subject can no longer benefit from the treatment; 5. General deterioration of health status and inability to continue study participation; 6. Major protocol deviations such as ineligibility found after enrollment; 7. Lost to follow-up; 8. Study termination by the sponsor; 9. Death; 10. Other reasons as determined by the investigator.
Determination of Sample Size	
In this study, IRC-assessed PFS (as per RECIST v1.1) will be used as the primary endpoint for superiority test with the control group. An interim analysis will be performed to determine the efficacy of the drugs and to determine whether to terminate or continue the study. The parameters for sample size calculation are as follows:
 
Enrollment rate = 13 subjects/month (156 subjects/year), enrollment time = 20 months (the overall time will be 26 months)
 
Randomization in a 1:1 ratio; one-sided $\alpha = 0.025$; the power of the test is 90%;
 
Hazard ratio (investigational treatment group/control group [HR]) = 0.64 (estimated median PFS is 4.5 months in the control group and 7.0 months in the investigational treatment group)
 
An interim analysis will be performed when 67% of PFS events are collected to determine the safety and efficacy of the drug by IDMC.
 
Based on the above parameters, at least 214 PFS events shall be collected according to the log-rank test for PFS comparison in the two groups and the O'Brien & Fleming spending function (EAST 6.4.1) in the α spending function method proposed by Lan-DeMets, i.e., approximately 262 subjects are needed. Considering a 10% dropout rate, 292 subjects are finally required for enrollment.

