1 REVISION

This statistical analysis plan is the initial version, drafted based on the final version of the study protocol (version no.: 3.0, version date: 25 Feb., 2019).

The final draft of this plan will be completed before database locking and will be signed by various functional departments for confirmation.

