3 STATISTICAL HYPOTHESES

A superiority test will be conducted to compare SHR-1210 combined with apatinib (treatment group) vs. doxorubicin combined with ifosfamide (control group) in improving the PFS (assessed by the IRC as per RECIST v1.1) of patients with soft tissue sarcoma, at a significance level of one-sided $\alpha = 0.025$. The null hypothesis (H_0) and alternative hypothesis (H_1) are:

H_0 : PFS hazard ratio (treatment group/control group) ≥ 1 ;

H_1 : PFS hazard ratio (treatment group/control group) < 1 .

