5.4 Efficacy analysis

5.4.1 Primary efficacy analysis

The primary endpoint of the study is the IRC-assessed PFS (as per RECIST v1.1). The primary analysis will be based on the FAS. The survival functions of PFS of the two groups will be compared using stratified log-rank tests with and without random stratification factors. The Kaplan-Meier method will be used to estimate the PFS rate, plot the survival curve, and estimate the median PFS, and its 95% CI will be calculated (Brookmeyer-Crowley method). The analysis with stratification factors will be used as the primary analysis.

In addition, as a supporting analysis and under the assumption of proportional hazards, the Cox models with and without stratification factors will be used to estimate the hazard ratio (HR) and calculate the corresponding 95% CI (Wald method).

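### SAP section 6 rules out the interim analysis that SAP 2.3 and protocol v3.0 both plan, so the stopping rule and the final test level are stated in conflict

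*SAP*

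**What the plan says.** **SAP.** Section 6 consists of one sentence: "No interim analysis will be conducted for this study". Section 2.3 says the opposite: "An interim analysis will be performed when 67% of PFS events (143) are collected", with a decision to terminate or continue. It then derives 214 events using the O'Brien-Fleming "spending function method proposed by Lan-DeMets, i.e., approximately 262 subjects are needed". Section 3 tests the primary hypothesis "at a significance level of one-sided" 0.025. Section 5.4.1 names the stratified log-rank test ("The analysis with stratification factors will be used as the primary analysis") but gives no nominal level. No interim or final boundary value appears anywhere in the SAP.

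**Origin and timing of the SAP.** Section 1 calls the document an initial version, "drafted based on the final version of the study protocol" (v3.0), and adds: "The final draft of this plan will be completed before database locking".

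**Protocol v3.0.** One efficacy look at 67% of PFS events is planned in three rows of the synopsis and in 14.1, 14.4.2, 14.4.6 and 14.4.8. The sample-size row of the synopsis gives its purpose as "to determine the safety and efficacy of the drug by IDMC". Table 12 sets z = -2.506 (HR 0.658, one-sided 0.006) at 143 events and z = -1.993 (HR 0.761, one-sided 0.023) at 214. Section 14.4.2 repeats the 0.023. Section 12.4 also describes the look but counts OS events, and the text of 14.4.6 once gives 166 events. Section 14.2 says that SAP revisions touching key content, such as endpoints or their analysis, are carried into the protocol.

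**The concern.** The two instructions cannot both be carried out. Under the protocol and SAP 2.3, the comparison is unblinded to the IDMC at 143 events and the trial ends early if the boundary is crossed. Under SAP 6 this does not happen. The final level depends on which applies: 0.023 if the look is taken, 0.025 if it is not. A final one-sided p-value between those two levels would be significant under one plan and not under the other.

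The trial is open-label, and the SAP promises to be final only before database lock. No document ties that point to the 143-event mark, so the question could still be open when the look falls due. If it is settled after comparative data have been seen, the sponsor can no longer show that the stopping rule and the final level were prespecified.

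**Working it through.** **Inputs** (SAP 2.3; protocol 14.1 and Table 12): one-sided α = 0.025, power 90%, 1:1 allocation, HR 0.64 (medians 4.5 and 7.0 months), 143 and 214 PFS events, 262 subjects before and 292 after 10% dropout, accrual over 20 of 26 months.

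**1. Reproduce Table 12.** The information fraction is t = 143/214 = 0.668.

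- Spending at the look: 2[1 − Φ(2.2414/√0.668)] = 0.00611, so z₁ = 2.506 and HR = exp(−2 × 2.506/√143) = 0.658.
- The final bound solves P(Z₁ ≥ 2.506 or Z₂ ≥ z₂) = 0.025 with correlation √0.668. This gives z₂ = 1.993, one-sided p = 0.0231, HR = exp(−2 × 1.993/√214) = 0.761.
- At 166/214 the same function gives z₁ = 2.293 and a final p of 0.0218, so the printed boundaries belong to 143 events.

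**2. Does 214 presuppose the look?** A single test needs 4(1.960 + 1.282)²/(ln 0.64)² = 211.02, so 212 events. With the look, 213 events give 89.93% power and 214 give 90.06%. The 214 is therefore the count with the look, two events more than a single test needs.

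**3. Operating characteristics at 214 events.** The drift is √(214/4) × |ln 0.64| = 3.264 at the end and 2.668 at the look.

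| | Look taken (2.506, then 1.993) | No look (1.960) |
|---|---|---|
| One-sided type I error | 0.0250 | 0.0250 |
| Power at HR 0.64 | 90.1% | 90.4% |
| Chance of stopping at 143 events, HR 0.64 | Φ(2.668 − 2.506) = 56.5% | none |

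**4. How often the verdicts differ.** P(Z₁ ≥ 2.506, Z₂ < 1.960) + P(Z₁ < 2.506, 1.960 ≤ Z₂ < 1.993):

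- HR 0.64: 0.00213 + 0.00543 = 0.00756
- HR 1: 0.00177 + 0.00177 = 0.00353

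**5. A mixture.** Taking the look at 2.506 and then testing the final at 1.960 gives an overall type I error of 0.0268. Neither document specifies this combination.

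**6. Time between 143 and 214 events.** Assumptions: exponential PFS with the stated medians, uniform accrual, exponential dropout at 0.0168 per month where used (10% lost before an event). The 27-month accrual is Sep 2018 to Dec 2020.

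| Scenario | 143 events (months) | 214 events (months) | Gap (months) |
|---|---|---|---|
| 262 over 20, no dropout (matches the plan) | 18.2 | 25.9 | 7.7 |
| 292 over 20, 10% lost | 17.7 | 25.1 | 7.4 |
| 292 over 27, 10% lost | 21.9 | 30.2 | 8.4 |
| 262 over 27, no dropout | 22.4 | 30.9 | 8.5 |

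**The case against.** The strongest reply is that the effect on the final inference is negligible. Either plan controls type I error, power differs by 0.3 percentage points, and the look costs two events. Across the two documents nothing is undefined: if SAP 6 governs, 0.025 is right and no boundary is needed; if the protocol governs, its boundaries and its rule for adjusting to the actual event count are already written. All of this stands. It means the missing boundary in the SAP is a consequence of the contradiction and not a second fault.

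SAP 6 may also be a deliberate later decision, with SAP 2.3 carried over from protocol 14.1. The SAP describes SHR-1210 as marketed where the protocol does not, and it drops OS and DoR from its objectives, so it does look later. But the SAP records no such decision, and protocol 14.2 expects a change of this kind to reach the protocol, where the look still stands.

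The time saving also needs its limits. The 7.7 months applies only if the trial stops early; the expected gain at HR 0.64 is 0.565 × 7.7, a little over 4 months. It is time to the event trigger, not study duration, which protocol 8.4 ties to 12 months after 214 events or complete OS data. At 18.2 months of a 20-month accrual, about 262 × 18.2/20 = 238 subjects would already be enrolled, so few would be spared. Finally, the IDMC charter is not available, and under 12.4 the IDMC recommends while the sponsor decides. None of these points tells the trial team whether the look takes place.

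**Conclusion.** The concern holds. The current texts give opposite instructions on whether a prespecified efficacy look on the primary endpoint is taken, and this must be settled before any comparative data are seen. The seriousness lies in the unresolved stop-or-continue rule, not in an error-rate fault in either plan. At stake are a 56% chance of stopping at 143 events if HR is 0.64, a gap of 7.4 to 8.5 months to the final event count under the stated accrual and dropout assumptions, and a final level of 0.023 or 0.025. The power and disagreement figures rest on proportional hazards at HR 0.64 and exactly 143 and 214 events.

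**What to change.** Before any comparative look, the sponsor states which plan applies and aligns every place that mentions it.

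- **If the look is kept:** replace SAP 6 with one look at 143 IRC-assessed PFS events (Lan-DeMets O'Brien-Fleming, z ≤ −2.506). Put the final one-sided 0.023, recomputed from the actual event counts, in SAP 3 and 5.4.1. In the same edit, correct the 166 in protocol 14.4.6 and the OS events in 12.4. Align the wording in SAP 2.3 and protocol 14.1 that the look may show the drug to be ineffective with Table 12, which has an efficacy bound only.
- **If the look is dropped:** remove it from SAP 2.3 and, by amendment, from the three synopsis rows and protocol 12.4, 14.1, 14.4.2, 14.4.6 and 14.4.8. State the final level as one-sided 0.025 at 214 events (90.4% power). Record when and why the look was dropped and that no comparative data had been seen.

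The cost is SAP wording plus small protocol corrections in the first case and one protocol amendment in the second. Neither needs patients or new data.
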